**Figure 7.a**  
**Labeling**

Set II Dilution #3 Mix A
 
Relez Therapeutics Use by (3.1.17)
	
Set II Dilution #3 Mix B
 
Relez Therapeutics Use by (3.1.17)
	
Set II Dilution #3 Mix C
 
Relez Therapeutics Use by (3.1.17)

---	---	---

#### *7.1.3.2 Investigational immunotherapy*

The investigational immunotherapy used in this study protocol will be prepared by the Johns Hopkins University School of Medicine Division of Allergy and Clinical Immunology Laboratory (DACI) a national reference laboratory facility according to institutional policy and in accordance with USP 797 compounding standards. The allergens that will be used to constitute the study immunotherapy solutions will be directly shipped by nationally licensed corporate suppliers such as Greerlabs, Lenoir NC 28645-0800 and Allergy Laboratories, Oklahoma, City. All allergens used in the compounding of study immunotherapy solutions will be FDA approved materials.

Sterile saline, used for the production of the study placebo solution will be supplied by the vendor compounding pharmacy. A comparable amount of glycerin and phenol as well as histamine will be added to the placebo vials to mimic any local irritant reactions that may occur in the active treatment vials.

#### *7.1.3.3 Storage*

Investigational immunotherapy solutions and placebo saline solutions will be refrigerated at 4 degrees celcius and stored in an appropriate, limited-access, secure place until it is used for the investigation or returned to the sponsor or designee for destruction. Storage will comply with the conditions specified on the label, and remain in the original container until dispensed. A daily temperature log of the drug storage area must be maintained every working day.

#### *7.1.4 Immunotherapy Dose and Regimen*

Recruited subjects alternate to be assigned either treatment set I or II (representing either placebo or active PMA treatment in a binded fashion). The assigned treatment set will remain for the duration of the study for each subject. On the day of an injection, 0.3ml from each of the appropriate vial set mix (A-C) will be combined in a sterile 5 ml bottle. Using a new sterile syringe, 0.15-0.60ml of the PMA solution or placebo will be removed for injection purposes according to the injection schedule (Appendix I). A sterile 27G ½ inch syringe will be used for administration. Immunotherapy will be administered bi-weekly in the study clinic for a total of eight consecutive weeks. Appendix I lists the precise immunotherapy injection schedule.

All patients are required to remain in the clinic under close observation by the study nurse for a period of 30 minutes following their injection. A physician is required to be present in the clinic at all times. In addition, one of the investigators must be present on campus and available by cell phone during scheduled treatment sessions. Emergency medications such as albuterol, oxygen, diphenhydramine, and at least two epi-pens will be readily available in the treatment area.

It is important to note that the maximum concentration of each individual allergen is quite low compared to more traditional immunotherapy regimens. The maximum PNU/ml (Protein Nitrogen Units) in vial #1 will be no more than about 180 PNU/ml per allergen (eg 0.9ml of 20,000 PNU/ml stock material into 100ml solution). In most cases the actual concentration of each stock allergen is much lower than 20,000 PNU/ml since the material may be provided as a mixture of several allergens. We would estimate therefore that subjects would receive no more than about 7.2 PNU of antigen contained in the highest injection (0.2ml Vial #2). Typically, allergens are administered via immunotherapy in a range of about 2000 PNU. Thus the dosage of each allergen is less than 0.36% of a typical dose administered in our clinics. The lower overall dosing scheme provided in this study would therefore be considered to be extremely safe with minimal adverse events.

#### 7.1.5 Overdose

An overdose is defined as a known deliberate or accidental administration of investigational immunotherapy to a study subject, at a dose above that which is assigned to that individual subject according to the study protocol.

All cases of overdose (with or without associated AEs) will be documented on an Overdose page of the CRF, in order to capture this important safety information consistently in the database. Cases of overdose without manifested signs or symptoms are not considered AEs. AEs associated with an overdose will be documented on an AE CRF according to Section 9.0, Pretreatment Events and Adverse Events.

Serious adverse events (SAEs) associated with overdose should be reported according to the procedure outlined in Section 9.2.2, Collection and Reporting of SAEs.

In the event of immunotherapy overdose, the subject should be treated symptomatically.

### 7.2 Investigational drug Assignment and Dispensing Procedures

A study subject randomization schedule will be developed by the study vendor compounding pharmacy or designee. In addition, stratification of study subject entry into the investigation will be determined by the study site investigators correlated with the study subject's clinical entry diagnostic criteria (see 6.1).

Subjects will be assigned to receive their treatment according to the randomization schedule provided to the study site by the vendor compounding pharmacy. The immunotherapy ID Number will be entered onto the study subject's CRF. All study immunotherapy will be administered to the study subjects while they are in the study site clinic.

Investigational immunotherapy blind maintenance will be undertaken by the vendor compounding pharmacy. During regularly scheduled monitoring visits, a study monitor from the sponsor or a designee will perform an inventory of blinded investigational immunotherapy solutions. All

unassigned treatment immunotherapy solutions will be reconciled and returned to the sponsor or a designee before study closure.

### **7.3 Unblinding Procedure**

The investigational drug blind shall not be broken by the investigator unless information concerning the investigational immunotherapy is necessary for the medical treatment of the subject. In the event of a medical emergency, if possible, the medical monitor should be contacted before the investigational immunotherapy blind is broken to discuss the need for unblinding.

For unblinding a subject, the investigational immunotherapy blind can be obtained by contacting the vendor compounding pharmacist. The sponsor must be notified as soon as possible if the investigational immunotherapy blind is broken. The date, time, and reason the blind is broken must be recorded in the study subject's source documents and the same information must be recorded on the subject's CRF. Investigational immunotherapy must be stopped immediately and the subject must be withdrawn from the study.

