### **6.4 Criteria for Discontinuation or Withdrawal of a Subject**

The primary reason for discontinuation or withdrawal of the subject from the study or study medication should be recorded in the CRF using the following categories. For screen failure subjects, refer to Section 8.1.11.

1. Pretreatment event (PTE) or adverse event (AE). The subject has experienced a PTE or AE that requires early termination because continued participation imposes an unacceptable risk to the subject's health or the subject is unwilling to continue because of the PTE or AE.
2. Significant protocol deviation. The discovery postrandomization or after the first dose of study immunotherapy that the subject failed to meet protocol entry criteria or did not adhere to protocol requirements, and continued participation poses an unacceptable risk to the subject's health.
3. Lost to follow-up. The subject did not return to the clinic and attempts to contact the subject were unsuccessful. Attempts to contact the subject must be documented.
4. Voluntary withdrawal. The subject (or subject's legally acceptable representative) wishes to withdraw from the study. The reason for withdrawal, if provided, should be recorded in the

CRF. All attempts should be made to determine the underlying reason for the withdrawal and, where possible, the primary underlying reason should be recorded.

5. Study termination. The sponsor, IRB, or regulatory agency terminates the study.
6. Pregnancy. The subject is found to be pregnant.

Note: If the subject is found to be pregnant, the subject must be withdrawn immediately. The procedure is described in Section 8.1.10.

7. The investigator has determined that continued participation would pose an unacceptable risk to the subject.

Note: After the 30 minute wait period, subjects that develop local swelling at the site of the injection greater than 50mm diameter will have their next dose decreased by one step. Subjects having a Grade 1-2 systemic reaction will have their next injection decreased by two steps. Systemic reaction Grade 3 or more will require withdrawal from the study. Systemic reactions are defined by the World Allergy Organization anaphylaxis grading system (13).

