### 8.3.4 Final Visit or Early Termination

The Final Visit will be performed on visit 18 or at an Early Termination Visit. The following procedures will be performed and documented:

- Physical examination.
- Vital signs.
- Concomitant medications.
- Concurrent medical conditions.
- Efficacy assessment.
- Safety assessment.
- Blood draw.

For all subjects receiving study medication, the investigator must complete the End of Study CRF page.

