#### 9.1.11 Action Concerning Study Medication

- Stop immunotherapy – the study immunotherapy is stopped due to the particular AE.
- Immunotherapy not changed – the particular AE did not require stopping the study immunotherapy.
- Unknown – only to be used if it has not been possible to determine what action has been taken.
- Not Applicable – the immunotherapy was stopped for a reason other than the particular AE eg, the study has been terminated, the subject died, dosing with the study immunotherapy was already stopped before the onset of the AE.

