#### **12.1.3 Efficacy Analysis**

The intent-to-treat approach will be used. Baseline characteristics will be described using mean and standard deviation for continuous variables and medians and ranges for discrete variables. The primary efficacy variable of comparing PMA versus placebo will be undertaken by quantifying the instrument-assessment scores of each study subject in each of the two therapeutic arms of the investigation. The p-value, least square (LS) treatment means, difference between the LS treatment means, and 95% confidence intervals for the treatment differences will be presented. The success of blinding will be assessed by asking the patient and staff which treatment set they thought they were getting, i.e. active treatment or placebo. The results will be recorded at each study visit.

Total Nasal Symptoms Score (TNSS) and the Mini-RQLQ attached in Appendix F will be used to evaluate clinical efficacy. TNSS along with rescue medication use is recorded at home on a daily

card as shown in Appendix K. Daily scores will only be recorded on weeks 2, 10, and 14. The mini-RQLQ will be recorded in person at screening, during each study visit, and at followup. The correct use of the TNSS survey is to score 0-12 based on symptoms reported that day while the mini-RQLQ is scored 0-84 based on symptoms reported over the past week. Higher scores indicate worse symptoms.

The primary outcome measure is the average daily combined score (DCS) which is calculated by adding the average TNSS + average medication score as well as the mini-RQLQ at weeks 2,10 and 14.

Secondary outcomes will include the adverse events rate and TNSS between both groups using a one-tailed Fischer's exact test and/or unpaired t test.

Other outcomes include baseline characteristics, use of epinephrine, and drop out between both treatment groups I and II using a one-tailed Fischer's exact test and/or unpaired t test. Trend tests for comparison of both groups will be performed such as the Jonckheere-Terptsra trend test. A sum of Mann-Whitney-Wilcoxon tests may also be sensitive and reveal a mild trend. Other trend tests may also be used.

A Kaplan-Meier or similar product limit estimator function will also be used to calculate the effect of treatment over time.

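### Unblinding, a Grade 3 or higher systemic reaction, or pregnancy removes a subject from the study and not only from treatment, so later outcomes needed for the stated intent-to-treat analysis are not collected

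*Combined protocol and SAP*

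**What the plan says.** Three events lead to mandatory withdrawal.

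- **Unblinding (section 7.3).** The blind may not be broken "unless information concerning the investigational immunotherapy is necessary for the medical treatment of the subject". Once it is broken: "Investigational immunotherapy must be stopped immediately and the subject must be withdrawn from the study". The sentence orders two separate acts, ending treatment and ending participation.
- **Systemic reaction (section 6.4).** "Systemic reaction Grade 3 or more will require withdrawal from the study".
- **Pregnancy (sections 6.4 and 8.1.10).** "If the subject is found to be pregnant, the subject must be withdrawn immediately". Section 8.1.10 names withdrawal and stopping immunotherapy side by side, so study withdrawal is the natural reading.

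On analysis, section 12.1.3 says: "The intent-to-treat approach will be used". Section 12.1.1 defines the full analysis set (FAS) as everyone randomised who had at least one dose. The SAP's four primary outcomes are the change in DCS and in mini-RQLQ from visit 2 to visit 17 and from visit 2 to visit 18, each compared by unpaired t test. Section 12.1.3 limits the daily diary to weeks 2, 10 and 14 and has the mini-RQLQ completed at each visit.

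For subjects who leave early, section 8.3.4 says: "The Final Visit will be performed on visit 18 or at an Early Termination Visit". Its procedures include an efficacy assessment.

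**The concern.** An intent-to-treat comparison needs outcomes from every randomised subject, whether or not treatment continued. Here the three events that force withdrawal also end outcome collection. Two of them are tied to clinical course. Unblinding is reserved for medical need, and a severe systemic reaction is an event of treatment. Subjects removed this way may differ from those who remain, and the difference may not be the same in both arms.

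If so, the visit 17 and 18 comparisons are made on a selected subset while being labelled intent-to-treat. With 18 subjects per arm, a few such losses can move the estimate. Neither section 12 of the protocol nor the SAP says how a missing visit 17 or 18 value is handled. By default, a t test on change scores drops the subject.

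**Working it through.** No figure in the plan is in dispute. The check has two parts: what a withdrawn subject can contribute, and how far the result could move.

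**1. What the primary tests need and what a withdrawn subject has.** I read diary weeks 2, 10 and 14 as serving visits 2, 17 and 18. The documents imply this pairing but do not state it. Appendix A starts treatment in week 3.

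| Time of withdrawal | DCS | mini-RQLQ |
|---|---|---|
| Weeks 3 to 9 | Baseline diary (week 2) only; no scheduled diary week after baseline | Up to the last visit attended; none at visits 17 or 18 |
| After the week 10 diary and visit 17 | Week 14 missing | Visit 18 missing |

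**2. Whether the Early Termination Visit fills the gap.** Section 8.3.4 offers it as the alternative to visit 18. It could give a mini-RQLQ score and perhaps a same-day symptom score. The DCS, however, is average daily TNSS plus average medication score over a diary week, and no diary week is attached to early termination. Nothing says whether an early-termination value may stand in for visit 17 or visit 18.

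**3. The plan's own sample size (section 12.3).** Inputs: 80% versus 30% response, alpha 0.05, power 80%, two-sided by section 12.1.1, allocation 1:1. With pooled variance and no continuity correction:

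n per arm = [1.96 × √(2 × 0.55 × 0.45) + 0.842 × √(0.8 × 0.2 + 0.3 × 0.7)]² / 0.5² = 14.3, rounded up to 15, or 30 in total.

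The plan states 28. At 14 per arm this formula gives 79.1% power, so the stated figure is reproduced closely enough.

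**4. Power.** Recruiting 36 for 28 evaluable allows (36 − 28)/36 = 22.2% loss from all causes.

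| Evaluable | Power, 80% vs 30% | Standardised difference detectable by t test, 80% power |
|---|---|---|
| 36 (18 per arm) | 88.9% | 0.96 |
| 28 (14 per arm) | 79.1% | 1.10 |
| 24 (12 per arm) | 71.9% | 1.20 |

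Losses within the allowance leave power near the target. Power is therefore not the main issue.

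**5. Bias.** For a mean score, suppose m of 18 subjects in an arm are unseen and their mean change would have differed from the completers' mean by Δ. The completer mean is then off by (m/18) × Δ, which is 5.6% of Δ for one subject and 22.2% for four.

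On the plan's response scale, assume L subjects lost per arm and 80% versus 30% among those who remain. The full-arm difference then lies between

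- lowest: [0.8(18 − L) − 0.3(18 − L) − L]/18
- highest: [0.8(18 − L) + L − 0.3(18 − L)]/18

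| Lost per arm | Lowest | Highest |
|---|---|---|
| 1 | (13.6 − 6.1)/18 = 41.7 points | (14.6 − 5.1)/18 = 52.8 points |
| 2 | (12.8 − 6.8)/18 = 33.3 | (14.8 − 4.8)/18 = 55.6 |
| 3 | (12.0 − 7.5)/18 = 25.0 | (15.0 − 4.5)/18 = 58.3 |
| 4 | (11.2 − 8.2)/18 = 16.7 | (15.2 − 4.2)/18 = 61.1 |

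The completers would show 50 points in every row. These are extreme bounds, not forecasts. The documents give no expected number of unblindings or forced withdrawals.

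**The case against.** A reader might infer more than the documents support, in five ways.

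- **That everyone who stops treatment must leave.** There is no such rule. Section 6.4 names the two separately: "The primary reason for discontinuation or withdrawal of the subject from the study or study medication should be recorded in the CRF". Section 9.1.11 has its own category for when "the study immunotherapy is stopped due to the particular AE", with no link to withdrawal. Section 8.2 only permits withdrawal for persistent non-attendance. Under section 6.4, large local reactions and Grade 1 to 2 systemic reactions change the next dose and do not end participation.
- **That outcome data are thrown away.** The FAS keeps every dosed subject, so data collected before withdrawal remain. Only later values are missing.
- **That safety follow-up is cut short.** Section 9.2.1.2 requires adverse events to be monitored until symptoms subside, and section 9.3 follows serious events to resolution or permanent outcome.
- **That the 8 extra subjects are a budget for these losses.** Section 12.3 gives them for drop-off in general.
- **That reactions will fall mainly on active treatment.** This is plausible, since the placebo contains no allergen, but no section states it.

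The strongest counter-argument is rarity. Section 9.1.4 reports no anaphylaxis or serious systemic reaction in more than 20,000 treated patients, and section 14.2 calls the chance of a serious allergic reaction very small. It is also fair to say that self-reported scores recorded after unblinding carry a bias of their own, so including them is a choice about what is being estimated.

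All of this limits the size of the problem. It does not supply the missing visit 17 and 18 values, and it does not say how their absence is handled.

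**Conclusion.** The concern holds for unblinding, Grade 3 or higher systemic reactions and pregnancy. For these subjects the protocol ends outcome collection along with treatment, while the analysis is called intent-to-treat and no missing-data rule exists. A subject withdrawn in weeks 3 to 9 has no scheduled diary from which to form a DCS after baseline.

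The consequence is possible treatment-related bias, of 5.6% of an arm per subject. The direction is unknown and the number affected may be small. The bounds in the working rest on an assumed equal loss of 1 to 4 per arm and on the plan's 80% and 30% response rates. This should be corrected because the change is cheap and follows the plan's own stated principle. It is not a reason to regard the trial as unsound.

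**What to change.** Leave every rule on when study treatment stops exactly as it is, and make these changes.

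1. **Sections 7.3 and 6.4, and 8.2 where withdrawal is discretionary.** Separate stopping study treatment from leaving the study. State that the remaining scheduled diary weeks and mini-RQLQ assessments are collected through visit 18 unless the subject withdraws consent.
2. **Primary analysis.** Include these data by randomised arm. Section 12.1.1, which now analyses efficacy by treatment received, has to be brought into line with this; that is a related but separate inconsistency.
3. **Sensitivity analysis.** Pre-specify one that excludes self-reported scores recorded after unblinding.
4. **Missing data.** State in the SAP how visit 17 and 18 values that are still missing are handled, and whether an Early Termination Visit score may be used.

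The cost is protocol and SAP wording plus a few follow-up contacts, using cards, questionnaires and visits that already exist. The downside is that some scores will come from subjects who know their treatment, which the sensitivity analysis is there to examine.

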### **7.4 Accountability and Destruction of Sponsor-Supplied Drugs**

Immunotherapy supplies will be counted and reconciled at the site before being returned to the sponsor or designee.

The investigator or designee must ensure that the sponsor-supplied immunotherapy solutions are used in accordance with the protocol and administered only to subjects enrolled in the study. To document appropriate use of sponsor-supplied immunotherapy solutions, the investigator or designee must maintain records of all sponsor-supplied study solutions supplied to the study site, site inventory, administration to each subject, and return to the sponsor or designee.

Upon receipt of sponsor-supplied drug, the investigator or designee must verify the contents of the shipments against the packing list. The investigator should ensure that the quantity is correct, and the solutions are in good condition. If quantity and conditions are acceptable, investigator or designee should acknowledge the receipt of the shipment from the vendor compounding pharmacy by signing the packing list and confirming by fax or e-mail while maintaining a record of the confirmation. The packing list should be filed in the investigator's essential document file.

The investigator or designee must maintain 100% accountability for all sponsor-supplied immunotherapy solutions during their entire participation in the study. Proper immunotherapy solutions accountability includes, but is not limited to:

- Continuously monitoring expiration dates if provided by the vendor compounding pharmacy
- Frequently verifying that actual inventory matches documented inventory.
- Verifying that the log is completed for the solutions administered to an individual study subject.

- Verifying that all immunotherapy solution containers used are documented accurately on the log.

Prior to site closure or at appropriate intervals, a representative from the sponsor or its designee will perform sponsor-supplied immunotherapy solutions accountability and reconciliation before sponsor-supplied solutions are returned to the vendor compounding pharmacy. The investigator or designee will retain a copy of the documentation regarding sponsor-supplied study solutions accountability, return, and/or destruction, and originals will be sent to the sponsor or designee.

The investigator will be notified of any expiry date of sponsor-supplied study solutions during the study conduct. On expiry date notification from the vendor compounding pharmacy, the site must complete all instructions outlined in the notification, including segregation of expired sponsor-supplied study solutions for return to the vendor compounding pharmacy for destruction.

